#### **Efficacy Parameters:**

Primary efficacy variable is response to treatment, which will be defined per the revised IWG response criteria for AML (Cheson, 2003) or standard response criteria for ALL (NCCN 2016 ALL response criteria).

The efficacy endpoints will be:

- CRc rate, including CR, complete remission with incomplete blood count recovery (CRi), and complete remission with incomplete platelet recovery (CRp)
- Morphologic leukemia-free state (MLFS)
- Partial remission (PR) rate
- Overall response rate (ORR) = CRc+PR
- DOR: Time from the first objective evidence of response to the first objective evidence of disease progression

---

- OS: Time from the date of enrollment to the date of death from any cause
- 30- and 60-day mortality rate

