#### Efficacy Analyses:

Response to treatment will be evaluated using the revised IWG response criteria for AML (Cheson, 2003) or the NCCN response criteria 2016 for ALL. The efficacy endpoints will be

---

CRc rate (including CR, CRi, and CRp), MLFS, PR rate, ORR, DOR, OS, and 30- and 60-day mortality rate.

For the binary efficacy endpoints, the point estimate and exact 95% confidence interval will be provided by dose level and overall. Time-to-event variables, such as DOR and OS, will be analyzed using the Kaplan-Meier method by dose level and overall.

The best overall response will be determined for each subject, in the order of CR, CRp or CRi, PR, and treatment failure (TF).

For each category as well as response (CRc or PR), the point estimate and 95% confidence interval will be calculated for the proportion, by dose level, and overall.

OS is the time from the first dose of DS-3201b to death. The censoring rules will be specified in the statistical analysis plan (SAP).

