##### **2.1.2.2. Part 2 (Dose Expansion)**

The secondary objectives of Part 2 are as follows:

1. To assess overall response rate (ORR) in subjects with relapsed/refractory AML and ALL using the revised International Working Group (IWG) response criteria and NCCN response criteria, respectively, duration of response (DOR), and OS.
2. To assess the PK after single and multiple doses of DS-3201b.

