- Duration of response (DOR): Time from the first objective evidence of response to the first objective evidence of disease progression
- Overall survival (OS): Time from the date of enrollment to the date of death from any cause
- 30- and 60-day mortality rate

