### 4.1. Enrollment

Subjects must sign and date the informed consent form (ICF) provided by the study sites before any study-specific qualification procedures are conducted.

Investigators will maintain a confidential screening log of all potential study candidates that includes limited information of the subjects (initials, age, sex), date, and outcome of screening process (eg, enroll in the study, reason for ineligibility, refused to participate).

Investigators will be expected to maintain an Enrollment Log of all subjects enrolled in the study indicating their assigned study number.

Investigators will maintain a confidential subject identification code list. This confidential list of names of all subjects who have been allocated to study numbers upon enrolling in the study allows the Investigator to reveal the identity of any subject when necessary.

Each subject or legally acceptable representative will be provided with information about the study, will have all questions answered to their satisfaction, and will sign and date an ICF. This will be completed before any study-specific procedures are performed. Additional information about informed consent procedures is provided in Section 1.6.2.

A subject is considered enrolled in the study upon the Investigator or designee obtaining written informed consent from the subject or the subject's legally acceptable representative (Section 1.6.2) and upon determination that all inclusion and exclusion criteria have been satisfied. After assigning a subject identification number (SID) to each subject at the timing of screening, Investigators will assess the eligibility of a subject based on the inclusion and exclusion criteria after obtaining written informed consent from the subject. After assessment by Investigators, the inclusion criteria/exclusion criteria form will be completed for registration.

The Sponsor will perform registration after verifying that the subject meets the inclusion/exclusion criteria provided by the Investigator. Directly after registration, the Sponsor will forward the results of registration to the Investigator. At this time, the subject will be assigned to study drug treatment.

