## 7. EFFICACY ASSESSMENTS

Efficacy assessments will be based on bone marrow assessments to be performed at Screening, Cycle 1 Day 8, and every cycle of treatment (ie, at start of Cycles 2, 3, 4, etc.) while the subject remains on study drug. The clinical activity of DS-3201b will be assessed using the revised IWG response criteria for AML or the NCCN Guidelines (Version 3.2013) for ALL (Section 17.3).

The efficacy endpoints will be:

- CRc rate (CR, CRi, and CRp)
- CR
- CRi or CRp
- MLFS
- PR rate
- ORR = CRc+PR
- DOR: Time from the first objective evidence of response to the first objective evidence of disease progression
- OS: Time from the date of enrollment to the date of death from any cause
- 30- and 60-day mortality rate

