### **11.4. Efficacy Analyses**

Response to treatment will be evaluated using the revised IWG response criteria for AML or the NCCN response criteria 2016 for ALL, respectively (Section 17.3). The efficacy endpoints will

be CRc rate (including CR, CRi, and CRp), MLFS, PR rate, ORR, DOR, OS, and 30- and 60-day mortality rate for AML and ALL, respectively.

For the binary efficacy endpoints, the point estimate and exact 95% confidence interval will be provided. Time-to-event variables, such as DOR and OS, will be analyzed using the Kaplan-Meier method by dose level and overall.

The best overall response will be determined for each subject, in the order of CR, CRp or CRi, PR, and treatment failure (TF). For each category as well as response (CRc or PR), the point estimate and 95% confidence interval will be calculated for the proportion.

OS is the time from the first dose of DS-3201b to the death. The censoring rules will be specified in the SAP.

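### OS has two start dates, and DOR as defined has no event for a responder who dies without progression; each needs one complete definition

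*Combined protocol and SAP*

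**What the plan says.** DOR and OS belong to the first secondary objective of Part 2 (Section 2.1.2.2: "duration of response (DOR), and OS").

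**OS.** Two origins are given.
- Enrollment: Section 3.1.3 has "Overall survival (OS): Time from the date of enrollment to the date of death from any cause". Section 7 has "OS: Time from the date of enrollment to the date of death from any cause", and the synopsis list of efficacy parameters says the same.
- First dose: Section 11.4 has "OS is the time from the first dose of DS-3201b to the death", and the synopsis paragraph on efficacy analyses has "OS is the time from the first dose of DS-3201b to death". The synopsis therefore disagrees with itself.

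**DOR.** Section 3.1.3 has "Duration of response (DOR): Time from the first objective evidence of response to the first objective evidence of disease progression", and the synopsis and Section 7 match it. No section names death as an ending event.

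**Early mortality.** The 30- and 60-day mortality rates are listed as endpoints without a start date.

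**Analysis.** Section 11.4 plans Kaplan-Meier for both time-to-event endpoints and leaves censoring rules to a separate SAP, whose text is not among the documents. Section 11.2 analyses efficacy on the Full Analysis Set. Section 11.1.3 limits that set to treated subjects with at least one post-baseline marrow assessment.

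**The concern.** The two OS origins are different dates. Section 4.1 counts a subject as enrolled on consent and "upon determination that all inclusion and exclusion criteria have been satisfied", which comes before dosing. Everyone in the efficacy set was dosed, so no analysed subject can die between enrollment and first dose. Choosing enrollment can only lengthen OS and, if the same origin is used for them, lower the early mortality rates. The result then depends on which section the programmer follows.

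For DOR, a response that ends in death is a response that has ended. A definition that stops only at progression leaves that outcome without an event. The natural Kaplan-Meier treatment is then to censor it, which treats the subject as if the response could have continued. That error runs one way, towards longer responses.

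Such deaths are plausible here. Section 1.4.1 reports 9 deaths in this study, of which 6 were in subjects with disease progression and 3 in subjects with other events such as sepsis and acute respiratory failure. It does not say whether any of the 3 were responders, so this gives no estimate of their frequency among responders. Section 3.1.4 also requires marrow evaluation after CR only when clinically indicated, so a death can precede any documented relapse.

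**Working it through.** **The plan's own figure.** Section 11.10 gives a 79.4% chance of 3 or more CRc among 20 subjects at a true rate of 20%. The exact binomial tail is 0.7939, so it reproduces. It does not depend on OS or DOR. The same inputs give the expected number of CRc responders per disease: 0.20 × 20 = 4.

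**OS origin.** The largest planned gap is about 14 days (screening windows in Sections 6.1.1 and 6.3.2.1). Section 1.2 cites a median OS of 3.8 months for induction-refractory AML and under 6 months for relapsed AML. One month is taken as 30.44 days.

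| Gap | 3.8 months (115.7 days) | 6 months (182.6 days) |
|---|---|---|
| 7 days (assumed) | 6.1% | 3.8% |
| 14 days (ceiling) | 14/115.7 = 12.1% | 14/182.6 = 7.7% |

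No benchmark is given for ALL.

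**Early mortality.** Assume exponential survival with a 3.8-month median from first dose, no death before dosing, and the same gap for every subject. Mortality at day t is 1 - exp(-ln 2 × t/115.7) from first dose. From enrollment, t is replaced by t minus the gap.

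| Origin | 30-day | 60-day |
|---|---|---|
| First dose | 16.5% | 30.2% |
| Enrollment, 7-day gap | 12.9% | 27.2% |
| Enrollment, 14-day gap | 9.1% | 24.1% |

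This shows sensitivity to the origin. It is not a forecast, and it ignores the marrow requirement of the Full Analysis Set.

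**DOR.** Let progression and death without progression have constant hazards hP and hD, with f = hD/(hP + hD).
- Median with death as an event: ln 2/(hP + hD).
- Median with those deaths censored: ln 2/hP.
- Ratio: (hP + hD)/hP = 1/(1-f).

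The documents give no f. Assumed values of 10%, 20% and 30% give 1.11, 1.25 and 1.43.

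**Sampling error.** If 4 responses end, the exponential 95% limits are the estimated median multiplied by 8/chi-square(0.975; 8 df) = 0.46 and 8/chi-square(0.025; 8 df) = 3.67. That range is far wider than 1.11 to 1.43. Partial remissions in AML would add responders, but the plan states no rate for them.

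**The case against.** The best case for leaving the text alone has five parts.

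1. Section 11.4, which governs the analysis, already starts OS at first dose, and either origin is usable. A reader might infer that OS is invalid as written. The documents do not support that: the defect is a contradiction between sections. It still stands, because three places say otherwise, including the endpoint definition itself.
2. A 14-day gap requires consent, all screening tests and the eligibility decision to be complete on Day -14. A reader might infer a 12.1% overstatement of OS. The documents give no distribution of gaps, so 14 days is only a ceiling.
3. No section says that a responder's death will be censored. Sections 1.6.3 and 11.2 let the SAP change planned methods. This is fair: the censoring is an inference from the definition. A SAP could change the definition openly, but a censoring rule alone sets neither the OS origin nor a new DOR event, and the protocol text would remain incomplete.
4. The DOR factors rest on an assumed f and constant hazards. They do not describe how a Kaplan-Meier median behaves with about 4 responders, so a reader should not take any one of them as this trial's bias.
5. Moving OS to first dose may seem to remove all guaranteed survival time. It does not. The Full Analysis Set also needs a post-baseline marrow, first scheduled at Cycle 1 Day 8 ± 2 days, so subjects who die before any such marrow stay excluded under either origin.

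**Conclusion.** The point holds in limited form and should be corrected. OS has two contradictory origins, differing by at most about 14 days per subject, and the enrollment origin can only lengthen OS. Early mortality has no origin at all. DOR ends only at progression; if deaths without progression are censored, it is biased upward by an amount the documents cannot fix.

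The consequence is confined to descriptive secondary estimates. No sample size or formal test rests on DOR or OS, and the expansion stopping rules in Section 3.1.8 use toxicity and ORR. With about 4 CRc responders per disease, chance variation exceeds the DOR bias. The reason to act is that the DOR bias would run in one direction, the OS text contradicts itself, and wording cures both.

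**What to change.** - **OS:** define it once, as first dose of DS-3201b to death from any cause, in both synopsis places and in Sections 3.1.3, 7 and 11.4.
- **30- and 60-day mortality:** state the same origin.
- **DOR:** define it as first documented response to the earliest of relapse, progression or death from any cause, in the synopsis and Sections 3.1.3 and 7. Relapse should be named because Section 4.2.1 groups it with progressive disease while Section 17.3.2 lists the two separately for ALL. Leave the other censoring rules to the SAP.
- **Full Analysis Set:** state beside the OS and mortality definitions that the first-dose origin does not remove the death-free period created by the post-baseline marrow requirement.

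Cost: a wording amendment, which under Section 15.1 goes through the same review and approval as the original protocol. No new data are needed, since long-term follow-up in Section 6.4 already collects date and cause of death. Reported estimates become somewhat shorter. Under the same assumptions, median DOR falls by the share f compared with censoring those deaths, and OS falls by up to about 14 days compared with the enrollment origin.

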### Best Response Measurement

Best response is defined to be the best-measured response (PR, MLFS, CRp or CRi, CR for AML, or CRi or CR for ALL). Best response will be evaluated for the full treatment period using all assessments up to and including treatment discontinuation.

#### **3.1.4. Disease Assessment**

Bone marrow biopsies/aspirates and blood samples for disease assessment will be performed according to the study schedule at baseline and on Cycle 2/Day 1 while the subject remains on study. If aplasia is observed on Cycle 2/Day 1 with no evidence of leukemia and absolute neutrophil count (ANC)  $<0.5 \times 10^9/L$  and platelets  $<20 \times 10^9/L$ , study drug may be withheld and a confirmation bone marrow assessment performed in 2 weeks. For subjects who achieve CR, a follow-up bone marrow evaluation is only required as clinically indicated. All subjects with less than CR must have a monthly bone marrow evaluation unless  $>5\%$  blasts are present in the peripheral blood, in which case bone marrow sampling is only required as clinically indicated. Additionally, based on the Investigator's clinical judgment, the frequency of bone marrow biopsies/aspirates can be reduced to once every 3 cycles after Cycle 3/Day 1 until Cycle 12/Day 1 (eg, Day 1 of Cycles 6, 9, and 12). After Cycle 12/Day 1, the frequency of bone marrow biopsies/aspirates can be reduced up to once every 6 cycles (eg, Day 1 of Cycles 18, 24, etc).

#### **Bone marrow re-biopsy at the End-of-study (EOS) treatment**

To search for possible mechanisms of acquired resistance to DS-3201b, an optional bone marrow re-biopsy may be performed within 30 days following the last dose of DS-3201b treatment for subjects who have achieved an initial CR/PR by standard response criteria but later developed progressive disease while on therapy (both in Dose Escalation and Dose Expansion), preferably prior to initiating new therapy.

#### **Bone marrow biopsies and leukemic cell enrichment**

- Bone marrow biopsies/aspirates and blood samples:

Bone marrow biopsies/aspirates or blood samples for disease status/response assessments, including flow cytometry and cytogenetics (per institutional guidelines and as clinically indicated), and exploratory resistance biomarker testing will be obtained as indicated in the study schedule.

For Part 1 and Part 2, a bone marrow evaluation is required for all subjects at screening.

- Leukemic cell enrichment:

Blood samples and bone marrow biopsies/aspirates will be collected pre-treatment at baseline for all subjects and/or at the EOS for subjects who achieve a CR or PR but develop recurrence or progression. Specimens of blood and marrow may be enriched for leukemic cells for further analysis.

Leukemic stem cell samples collected from pre- and post-dose bone marrow aspirates will be quantified by flow cytometry and/or mass cytometry and blood and/or bone marrow cells may be examined for H3K27me3 status.

### **3.1.5. Duration of the Study**

The study duration is expected to last approximately 5 years from the time the first subject is enrolled in Part 1 of the study and including the LTFU Period.

### **3.1.6. Duration of Subject Participation**

The number of treatment cycles is not fixed in this study. Subjects who continue to derive clinical benefit from treatment in the absence of withdrawal of subject consent, progression, or unacceptable toxicity may continue treatment cycles. Subjects in Part 1 and Part 2 who are still on study at least 6 months after enrollment of the last subject in the study may be eligible to continue receiving study drug in a separate extension phase of the protocol (see Section 17.9). Data collected from those subjects may be captured in a separate database.

### **3.1.7. Stopping Rules**

The Sponsor has the right to terminate the study at any time and study termination may also be requested by (a) competent authority(ies). Additional consideration includes any frequency in TEAEs that may reflect subject deterioration or further compromise including fatal outcome or which may be related to the overall efficacy of study therapy. Please also see the DLT definition (Section 3.1.7.2) and the stopping rules during dose expansion (Section 3.1.8).

#### **3.1.7.1. Stopping Rule for Maximum Tolerated Dose Determination**

The final MTD will be decided based on considerations of the MTD estimated by the BLRM, and on an overall assessment of safety data from subsequent cycles and of PK/PD response collected at all different doses tested. For dose determination, the following stopping rules will be implemented for the Dose Escalation part: (a) at least 6 evaluable subjects at the MTD level with at least 21 evaluable subjects in total enrolled in the Dose Escalation part, (b) at least 9 evaluable subjects have been enrolled at a dose level which is the model's recommendation for the next dose cohort and for which the posterior probability of targeted toxicity is at least 50%, or (c) dose level 1 is too toxic.

#### **3.1.7.2. Dose-limiting Toxicities**

Dose-limiting toxicity is defined as a clinically significant non-hematologic TEAE or abnormal clinical laboratory value that is clearly not related to disease progression, intercurrent illness, and occurring during the first cycle (28 days) on study that meets any of the following criteria:

- National Cancer Institute (NCI) – Common Terminology Criteria for Adverse Events (CTCAE), Version 4 Grade 3 aspartate aminotransferase (AST) (SGOT), alanine aminotransferase (ALT) (SGPT), or bilirubin for  $\geq 7$  days.
- NCI-CTCAE Grade 4 AST (SGOT) or ALT (SGPT) of any duration.
- All Grade 4 non-hematologic toxicities of any duration.
- Any Grade 5 toxicity, unless proven to be clearly and incontrovertibly related to disease progression or intercurrent illness will constitute a DLT.
- All other clinically significant, non-hematological NCI-CTCAE Grade 3/4 AEs.

Exceptions are as follows:

- Grade 3 or 4 nausea, vomiting, and diarrhea that do not require hospitalization or total parenteral nutrition (TPN) support and can be managed with supportive care to  $\leq$ Grade 2 within 48 hours.
- Alopecia and study drug-related fever will not constitute DLT.
- Grade 3 or 4 electrolyte abnormalities that are corrected to  $\leq$ Grade 2 within 24 hours.
- Grade 3 or 4 differentiation syndrome which improves to  $\leq$  Grade 1 within 7 days of the start date of  $\geq$  Grade 3 differentiation syndrome and which is not associated with end-organ damage.

Myelosuppression and associated complications are expected events during leukemia therapy. Only prolonged myelosuppression, as defined by absolute neutrophil count (ANC)  $<0.5 \times 10^9/L$ , platelets  $<20 \times 10^9/L$ , and marrow cellularity  $<5\%$  on Day 42 or later (6 weeks) from start of therapy without any evidence of leukemia will be considered in defining the MTD and DLT. DLT evaluation of myelosuppression will be decided between the Investigators and Sponsor Medical Monitor during safety review meetings.

Subjects who are unable to complete at least 75% of the prescribed dose (ie, 21 days) of DS-3201b during the DLT evaluation period as a result of non-disease-related  $\geq$ Grade 2 AEs will be considered to have a DLT.

### **3.1.8. Maximum Tolerated Dose and Recommended Dose for Expansion Definition**

Once the stopping criteria are met, the MTD estimated by BLRM + EWOC is the dose with the highest posterior probability of the DLT rate in the target DLT rate interval of [16%, 33%] among all doses fulfilling the following 2 constraints:

- The overdose control constraint: There is less than a 25% probability for the DLT rate  $>33\%$  (probability for excessive or unacceptable toxicity) (Section 3.1.2.1);
- The mean of the posterior distribution of DLT target rate at this dose is  $\leq 25\%$ .

Since an alternative drug administration schedule may be explored in lieu of or in parallel with the original QD  $\times$  28/28 days schedule, separate MTDs may be identified for each regimen. The final MTD for each dosing schedule will be decided based on considerations of the respective MTDs estimated by the BLRM and on an overall assessment of safety data from subsequent cycles and PK/PDy response information collected at all different doses tested. Upon determining the final MTD of the original QD  $\times$  28/28 days and/or alternative dosing schedules, 1 dosing regimen will be selected for further evaluation in Part 2 (Dose Expansion). This regimen given at the final MTD determined in Part 1 is referred to as the “Tentative Recommended Dose for Expansion”.

In the Dose Expansion cohort, the safety will be assessed continuously after 4 subjects are enrolled in each cohort of AML and ALL. The study will be stopped if the cumulative incidence of clinically relevant  $\geq$ Grade 3 toxicities exceed 30%. The exceptions are:

- Grade 3 and higher nausea, vomiting, or diarrhea that do not require hospitalization or TPN support and can be managed with supportive care to  $\leq$ Grade 2 within 48 hours.

- Alopecia and study drug-related fever.
- Grade 3 or 4 electrolyte abnormalities that are corrected to  $\leq$ Grade 2 within 24 hours.
- Grade 3 or 4 differentiation syndrome which improves to  $\leq$  Grade 1 within 7 days of the start date of  $\geq$  Grade 3 differentiation syndrome and which is not associated with end-organ damage.

Evaluation of myelosuppression will be decided between the Investigators and Sponsor Medical Monitor during safety review meetings.

In the Dose Expansion cohort, the efficacy will be assessed continuously after 10 subjects are enrolled. The study will be stopped if the cumulative ORR will be less than 10%.

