### 11.11.2. Prior Specification for Bayesian Logistic Regression Model Parameters

The Bayesian approach requires the specification of a prior distribution for the BLRM parameters. A minimally-informative bivariate normal prior for the model parameters ( $\log(\alpha), \log(\beta)$ ) is obtained as follows:

- The best guess of MTD is projected to be around 700 mg in humans. The median prior probabilities of DLT are set to be approximately 8% and 24% at 100 mg (projected starting dose for dose escalation using BLRM) and the projected MTD of 700 mg, respectively.
- For the remaining doses, the prior medians of probability of DLT are assumed linear in log-dose on the logit-scale.
- Based on the above medians for the probability of DLT at each dose and wide prior credible intervals (obtained from minimally informative beta distributions), the optimal parameters of the bivariate normal distribution can be obtained as follows:

Parameters	Means	Standard deviations	Correlation
$\log(\alpha), \log(\beta)$	(-1.005, -0.093)	(1.289, 1.098)	-0.182

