### 11.11.3. Escalation with Overdose Control Principle

Dose recommendation for the next cohort will be based on summaries of the posterior probability of the DLT rate for possible doses: 100 mg, 150 mg, 250 mg, 350 mg, 500 mg, and 700 mg, and if MTD has not been reached, 1000 mg. The above dose levels are only a guideline, and the exact dose level for the next dose escalation cohort will be determined after reviewing the available safety and study data from all enrolled subjects. After the first 3 subjects of each cohort complete the DLT evaluation during Cycle 1, the posterior distributions of the DLT rate will be derived for all provisional dose levels based on the BLRM using the DLT outcome data from all assessed doses and a pre-specified prior distribution for the model parameters. The posterior probability of the DLT rate in the following 4 intervals at each dose level ([0%, 16%) as the DLT rate interval for under-dosing, [16%, 33%) as the target DLT rate interval, [33%, 60%) as the DLT rate interval for excessive toxicity, and [60%, 100%) as the DLT rate interval for unacceptable toxicity) will then be calculated and used for dose recommendation for the next cohort according to the EWOC principle. It is therefore conceivable that the posterior probability of DLT rate for dose recommendation may be generated using alternative provisional doses as long as the predicted exposure increments are between 30% and 100% (Section 3.1.2.1).

The EWOC principle requires that the BLRM recommended dose for the next cohort of subjects is defined as the highest posterior probability of the DLT rate in the target DLT rate interval [16%, 33%) among all doses fulfilling the overdose control constraint: there is less than a 25% probability for the DLT rate >33% (probability for excessive or unacceptable toxicity).

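### The escalation stopping rules can stop at a dose that the Section 3.1.8 MTD definition then excludes, because the two use different admissibility tests

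*Combined protocol and SAP*

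**What the plan says.** Escalation ends under Section 3.1.7.1 (repeated in the synopsis and 3.1.2.1) when one of three rules is met. Rule (a) needs 6 evaluable subjects at the MTD level and 21 in total. Rule (b) needs "at least 9 evaluable subjects have been enrolled at a dose level" that is the model's next recommendation, provided that the "posterior probability of targeted toxicity is at least 50%, or (c) dose level 1 is too toxic", the last clause being rule (c).

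The model's recommendation is defined in 3.1.2.1 and 11.11.3. It is the dose with the highest probability of a DLT rate in 16–33%, "among all doses fulfilling the overdose control constraint: there is less than a 25% probability for the DLT rate" above 33%. That is a single test.

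Section 3.1.8 applies once escalation has stopped. It picks the dose with the highest target probability "among all doses fulfilling the following 2 constraints". The first is the same overdose test. The second is new: "The mean of the posterior distribution of DLT target rate at this dose is" no more than 25%. I read this as the posterior mean DLT rate.

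The estimate is not binding: "The final MTD will be decided based on considerations of the MTD estimated by the BLRM", together with later-cycle safety and PK/PDy data.

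**The concern.** A dose can pass the overdose test and fail the mean test. Escalation may then be declared complete, with 9 evaluable subjects at a dose that the MTD definition rejects. The slope is constrained to be positive (11.11.1), so the posterior mean rises with dose and every higher dose fails as well. Only two outcomes remain: a lower dose becomes the estimated MTD, or no dose qualifies.

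Only rule (a) sets a minimum number of subjects at the MTD, and the plan does not define MTD level before stopping. If it means the 3.1.8 MTD, rule (a) is safe and rule (b) carries the gap. If it means the current EWOC recommendation, rule (a) has the same gap. The text requires no further subjects at the lower dose and does not say what follows if no dose qualifies.

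Finding the MTD and RDE is a primary objective of Part 1. Section 11.10 expects 6 to 9 escalation subjects at the RDE, and nothing secures that number after such a stop.

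**Working it through.** **Inputs.** Model from 11.11.1: logit π(d) = log α + β log(d/700). Prior from 11.11.2: (log α, log β) bivariate normal, means (−1.005, −0.093), SDs (1.289, 1.098), correlation −0.182. Doses from 11.11.3: "100 mg, 150 mg, 250 mg, 350 mg, 500 mg, and 700 mg, and if MTD has not been reached, 1000 mg". Posteriors were computed by grid integration.

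**The plan's own figure.** The plan gives no operating characteristics for escalation. The figure that can be checked is the prior: "The median prior probabilities of DLT are set to be approximately 8% and 24% at 100 mg" and 700 mg respectively. At 700 mg the printed parameters give 1/(1 + e^1.005) = 1/3.732 = 26.8%. At 100 mg, integrating over β, they give 4.6%. The stated medians are therefore not reproduced, so I also used two re-set priors with the same SDs and correlation. In both, the mean of log α is ln(0.24/0.76) = −1.153. The mean of log β is −0.640 (exact medians 8.0% and 24.0%) or −0.411 (plug-in slope; medians 6.2% and 24.0%).

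**Examples**, cohorts of 3, one level at a time, DLTs/subjects in ascending dose order from 100 mg:

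| Case | Data | Prior | Stop dose | P(16–33%) | P(>33%) | Mean | 3.1.8 MTD (n) |
|---|---|---|---|---|---|---|---|
| 1 | 0/3, 0/3, 1/3, 3/9 | printed | 350 mg | 0.605 | 0.222 | 0.256 | 250 mg (3) |
| 2 | 0/3, 0/3, 0/3, 1/3, 3/9 | printed | 500 mg | 0.596 | 0.243 | 0.262 | 350 mg (3) |
| 3 | 2/9, 0/3, 3/3 | printed | 100 mg | 0.565 | 0.239 | 0.257 | none |
| 4 | 0/3, 0/3, 3/9, 2/3 | both re-set | 250 mg | 0.617–0.618 | 0.246–0.248 | 0.266–0.267 | 150 mg (3) |
| 5 | 0/3, 0/3, 2/9, 3/3 | both re-set | 250 mg | 0.615–0.617 | 0.236–0.240 | 0.262–0.264 | 150 mg (3) |

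In case 1 the model recommends 350 mg after each of the last four cohorts. All parts of rule (b) are met: 9 subjects, recommended dose, target probability above 0.50. The total is 3 + 3 + 3 + 9 = 18, so rule (a) cannot apply on either reading. The mass below 16% is 1 − 0.605 − 0.222 = 0.173, too little to pull the mean under 0.25. At 250 mg the mean is 0.201, so that dose qualifies, with 3 subjects.

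Case 2 has 3 + 3 + 3 + 3 + 9 = 21 subjects. If MTD level means the EWOC recommendation, rule (a) is met at 500 mg too, with the same conflict.

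**Frequency.** The plan gives no true DLT rates, so these are assumptions: curves logistic in log-dose, 25% DLT at 250, 350, 500, 700 or 1000 mg, slope 1.0, 1.5 or 2.5, at most 60 subjects. The 3.1.8 MTD is limited to tested doses.

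- Rule (a) refers to the 3.1.8 MTD, conflict stops under (b). Cohorts of 3: 0.3–12.7% of trials (printed prior), 0.1–10.8% (re-set). Cohorts varying from 3 to 6: 0.5–7.9% and 0.5–9.0%. Cohorts of 6: 0–0.8% and 0–2.1%.
- Rule (a) refers to the EWOC recommendation, cohorts of 3: about 0–5% under (b) and about 11–21% under (a).
- On the first reading, the estimated MTD has fewer than 6 subjects in 72–100% of conflicts with cohorts of 3, and never with cohorts of 6.
- No dose qualifies in at most 0.5% of trials under these curves, and in up to 1.9% if the true rate at 100 mg is 28%.

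**The case against.** The strongest reply is that the model MTD is only one input. The final MTD also weighs later-cycle safety and PK/PDy. Section 3.1.2.1 lets cohorts at or below the MTD grow to 20 in order to define the RDE. Part 2 adds about 20 subjects per disease, with a safety review after the first 4. All DLT data inform the estimate at every dose. This stands as mitigation. It does not close the gap, because expansion is optional and the two written rules still name different doses. The Cohort Management Plan cited in 3.1.2.1 is not available and may say more.

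Second, the two-DLT clause in 3.1.2.1 may trigger re-evaluation before a third subject enters, and cases 3 and 5 need a cohort with 3/3 DLTs. With 2/2 instead, their means fall to 0.226 and to 0.228–0.230, and the conflict goes. That is fair for those cases. Cases 1, 2 and 4 need no such cohort. Cases 1 and 2 do depend on the printed prior: under the re-set priors the mean is 0.246–0.248 in case 1 and 0.244–0.2495 in case 2. Case 4 fails the overdose test under the printed prior (P(>33%) 0.254). Each prior thus has an example free of a 3/3 cohort, although none of the five shown serves for all three priors.

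Third, the dose list in 11.11.3 is only a guideline, so an intermediate or lower dose could be used when none on the list qualifies. That stands, and the no-dose outcome should carry little weight.

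A reader might also infer that rule (b) alone is at fault. The text does not settle what MTD level means in rule (a), so that inference is not supported.

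**Conclusion.** The mismatch is real and follows from the written rules without any assumed DLT curve. Its frequency does depend on the assumed curves, the cohort size, the prior and the reading of rule (a), as the ranges show.

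The consequence is modest. With at most 5 DLTs the excluded dose has a posterior mean of 0.250–0.268, and up to 0.283 on longer paths, against a limit of 0.25. The definition moves the MTD down. The cost is an estimated MTD resting on few subjects, not excess toxicity.

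Two stronger readings are tempting. One is that an over-toxic dose would go into Part 2. The documents do not support it: the rejected dose has already passed overdose control, and 3.1.8 points to a lower one. The other is that this trial ended in the conflict. Section 1.4.1 reports 3 DLTs, one at 700 mg/day, and gives no counts per dose; cases 1 to 5 never reach 700 mg. From states compatible with those facts and the 22 AML/ALL subjects in 1.1.1.6, the later chance with cohorts of 3 (first reading) is 0–8.1% with the printed prior and 0–11.4% with the re-set ones.

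The change should be made, but it is not critical to safety.

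**What to change.** In the synopsis, 3.1.2.1 and 3.1.7.1, state that the dose in both rules (a) and (b) must be the tested dose that satisfies both 3.1.8 constraints. Changing rule (b) alone would leave the second reading of rule (a) open. In 3.1.8, say that the candidates are doses tested in the trial.

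If the recommended dose has enough subjects but fails the mean test, assign the next cohort to the tested dose that is the 3.1.8 MTD. Say in 11.11.3 that this overrides the usual recommendation for that cohort; otherwise 11.11.3 would still point to the higher dose.

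If no tested dose meets both constraints, apply rule (c) or go to a lower dose. The 25 mg capsules in 5.1 allow 75 or 50 mg.

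The cost falls only on affected trials. With rule (b) corrected on the first reading, they enrol on average 3.0–3.5 more subjects with cohorts of 3, 4.1–5.1 with cohorts of 3 to 6, and 6 with cohorts of 6. The final estimated MTD then has at least 6 subjects in 98–100% of them (85–100% with cohorts of 6, where nearly all the rest end with no admissible dose). On the second reading more trials would need the extra cohort.
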